### **11.3 Patient wishes**

Should the subject wish to withdraw from the study, he/she may do so at any time. The subject may then continue to receive standard of care.

### **11.4 Investigator discretion**

Should the subject no longer meet eligibility criteria, or should [name] deem the treatment inappropriate for the subject, he may elect to withdraw the subject at any time.

## **12.0 DATA REPORTING**

Screening:

Approved, watermarked ICFs will be used to consent patients prior to enrollment in the study.

At the screening visit the subject will sign ICFs (main and photo) and HIPAA forms. An investigator will also assess eligibility using source documents provided (see

appendix VII). Patient will be entered into Velos as per University of Miami policy and HIPAA forms will be faxed to the UM Office of HIPAA Privacy & Security.

#### During Therapy:

At each treatment session, the investigator will complete the appropriate source documents relevant to each visit. The data from these source sheets may be entered into master document (excel spreadsheet on locked computer) up to 21 days from time of visit. Source documents can be seen in Appendix VII.

#### Follow-up:

One week after final excisional biopsy, subjects will return for wound check and final follow-up. Follow-up source document will be completed at that time. (see Appendix VII).

#### Completion:

After the final follow-up visit, subjects' completion of involvement in study will be documented in Velos, as per University of Miami Policy.

All paper documents listed above will be stored in a labeled binder that will be kept in a locked filing cabinet within our office. Only people listed on eProst will have access. Computer data will be kept in an excel file in a locked computer in our office. Only people listed on eProst will have access.

Data must be submitted according to the protocol requirements for ALL subjects receiving treatment. Subjects for whom documentation is inadequate to determine eligibility will generally be deemed ineligible.

A list of forms to be submitted, as well as expectation dates, may be found in Appendix IV.

## **13.0 STATISTICAL CONSIDERATIONS**

### **13.1 Study Design/Objectives**

This is a prospective, unblinded, randomized, two-arm (treatment arm vs Control/non-treatment arm) pilot study to determine whether the 595/1064 nm laser merits further study for efficacy in the treatment of basal cell carcinoma. The primary objective of the study is to preliminarily assess the efficacy of the 595/1064 nm multiplex laser for the treatment of superficial and

nodular basal cell carcinomas less than 1.5 cm in size. Our primary endpoint will be the overall response rates (CR+PR), as defined in section 9.0.

The secondary objective of this study is to assess the safety and side effect profile of the multiplex laser for this indication.

### 13.2 Sample Size Justification/Accrual Rate

The analysis set (evaluable subjects) consist of study-eligible subjects who either complete three treatments/three study visits and the biopsy visitor are withdrawn from the study due to showing evidence of PD during the study (non-responder). Subjects will be non-evaluable when they do not wish to continue in the study, are unable to continue in the study, or they cannot complete treatments or study visits for any reason other than PD. There will be 15 evaluable subjects in the treatment arm and 5 evaluable subjects in the control (non-treatment) arm. We expect that three to four subjects in both treatment arm and control arm will be non-evaluable. Therefore, the planned maximum number of enrolled subjects will be 28. The number of subjects is small due to the preliminary nature of the study, yet similar in size to previous studies (Konnikov et al 2011 and Shah et al 2009), which only used the 595 nm laser. Out of our 15 subjects in the treatment arm, we expect eleven or more subjects will respond to proposed treatment (either CR or PR). The table below shows significance (p-value) of hypothetical study findings assuming one BCC per subject. As shown in the second row, if one out of five subjects in the control arm shows either CR or PR and twelve or more out of fifteen subjects in the treatment arm show either CR or PR then test of comparing proportions of two arms is statistically significant (p-value < 0.05). If none in the control arm show either CR or PR and nine or more out of fifteen subjects in the treatment arm have either CR or PR, we also get a statistically significant difference indicating a better response rate in the treatment arm.

Number of subjects (CR or PR) among 15 subjects in the treatment arm vs. 5 in control arm	p-value*
11 (73.3%) vs. 1 (20%)	0.058
12 (80%) vs. 1 (20%)	0.031
9 (60%) vs 0 (0%)	0.030

\* one-sided Fisher's exact test (assuming every subject has one BCC)

One to two subjects will be accrued per week secondary to availability of the laser.

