##### **3.3.2.1 Cancellation Guidelines**

If a subject does not complete protocol therapy or no longer wishes to receive therapy, the subject may withdraw. [name] may also

withdraw patients if it is in their best interest. Subjects who are enrolled on study but not treated will be excluded from all analyses.

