#### **4.1 Agent Administration**

**Subjects in the treatment arm** will receive 3 treatments using the 595/1064 multiplex laser spaced by a four-week interval (+/- 7 days), administered in an outpatient clinic setting. Prior to treatment, the area will be cleaned and dried. Application of a topical anesthetic will not be necessary but is available upon request.

The treatment settings for each laser session will be as follows:

595 nm PDL at a fluence of 10 J/cm^2, a 10 ms pulse duration, and a 10 mm spot size. After a 500 msec interpulse delay, a second pulse with 1064 nm laser at a fluence of 40 J/cm^2, 10 ms pulse duration, and 10 mm spot size will be administered; the BCC lesion will be treated using 10% overlap with a single pass, along with 4 mm of normal skin. Dynamic cooling feature (cool air) will be provided.

**Subjects in the control arm** will not receive any treatment; however they will receive 3 regular study visits spaced 4 weeks (+/- 7 days).

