## **6.0 DOSING DELAYS/DOSE MODIFICATIONS**

### **6.1 Study Agent**

There are no expected dosing delays or dosing modifications for this study. Due to the fact we are testing specific laser parameters for the potential efficacy of clearing certain types of basal cell carcinomas, we will not be adjusting the settings.

However, should the subject experience any adverse effects secondary to the use of the multiplex laser, they will immediately be provided with supportive care tailored to the nature of the adverse effect (see section 4.2). In addition, there are no expected systemic toxicities. If the expected and unexpected effects are not tolerable, the subject may also withdraw from the study at any point.

In our study, early termination will be based on presence of intolerable side effects and desire to withdraw from studies. Should our treatment prove ineffective, all patients will receive standard treatment of care immediately.

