### **11.2 Unacceptable Adverse Events**

Likely side effects to treatment with this laser may include pain of the skin, erythema, purpura, or temporary hypo or hyperpigmentation of the skin. Unlikely reported side effects include hematoma, scarring, mild skin ulceration or bullous dermatitis, and skin infection. See section 7.1.12.

Any grade III non-lab toxicities that are possible, probably or definitely related to involvement in the study are unacceptable and subjects will receive immediate supportive care and be withdrawn from the study.

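### The single analysis set in 13.2 drops laser subjects who stop for toxicity or intolerance, which can overstate the laser response rate and bias the randomized comparison; 3.3.2.1 also conflicts with analysing controls

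*Combined protocol and SAP*

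**What the plan says.** Section 13.2 defines the evaluable set as study-eligible subjects who complete three treatments or study visits and the biopsy visit, or who are withdrawn for progression and counted as non-responders. Everyone else is out: "Subjects will be non-evaluable when they do not wish to continue in the study, are unable to continue in the study", or if they "cannot complete treatments or study visits for any reason other than PD".

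Other sections decide who takes that route:

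- Section 11.2, on related grade III non-laboratory toxicity: "subjects will receive immediate supportive care and be withdrawn from the study".
- Section 6.1: "early termination will be based on presence of intolerable side effects and desire to withdraw from studies".
- Section 4.2.1: a subject who starts a prohibited medication is removed or is not evaluable for response. This can happen in either arm.

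Controls, under section 4.1, "will not receive any treatment; however they will receive 3 regular study visits". Section 13.2 expects three to four non-evaluable subjects in each arm and a maximum enrolment of 28. Sections 13.2 to 13.5 plan no all-randomized analysis and no sensitivity analysis for missing outcomes.

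Section 3.3.2.1 adds a second exclusion: "Subjects who are enrolled on study but not treated will be excluded from all analyses".

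**The concern.** The primary endpoint is response (CR or PR), compared between randomized arms. Removing subjects for events after randomization means that the groups compared are no longer the groups randomized. Here one cause of removal, inability to tolerate the laser, cannot occur in the control arm. If those subjects would mostly not have responded, the laser response rate is inflated, and that is the figure on which a larger trial would be planned. With 15 v 5 evaluable subjects, a few exclusions can move the test across 0.05.

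The sentence in 3.3.2.1 is a separate problem. Controls are enrolled and not treated, so the literal rule removes the whole comparator that 13.2 and 13.3.2 set out to analyse. It also removes anyone randomized to the laser who leaves before the first session.

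**Working it through.** **Inputs.** Section 13.2 gives 15 laser and 5 control evaluable subjects, three to four lost per arm, a maximum of 28, and illustrative results of 11 v 1, 12 v 1 and 9 v 0 responders. Section 13.3.2 gives the one-sided Fisher's exact test and exact binomial 95% intervals when every subject has one BCC. That case is assumed throughout.

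**Enrolment.** 15 + 4 + 5 + 4 = 28, so the maximum implies four losses in each arm, from 19 laser and 9 control subjects. That is 4/19 = 21% of laser subjects, 4/9 = 44% of controls and 8/28 = 29% overall. The 3:1 allocation in 3.3.3 would instead split 28 as 21:7; 19 and 9 are used below because they are what 13.2's own counts require.

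**The plan's own figures.** For 12/15 v 1/5 there are 13 responders among 20 subjects, so

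p = [C(13,12)·C(7,3) + C(13,13)·C(7,2)] / C(20,15) = (455 + 21)/15504 = 0.0307.

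The same test gives 0.0578 for 11 v 1 and 0.0298 for 9 v 0. All three match the table in 13.2 (0.031, 0.058, 0.030).

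**Laser response rate with 12 responders (exact 95% CI).**

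- As planned: 12/15 = 80% (52–96%).
- Four losses counted as non-response: 12/19 = 63% (38–84%).

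**The test under different handling of losses, 12 v 1 observed responders.**

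| Handling | Laser | Control | One-sided p |
|---|---|---|---|
| As planned | 12/15 | 1/5 | 0.031 |
| One laser loss as non-response, no control losses | 12/16 | 1/5 | 0.048 |
| Two laser losses, no control losses | 12/17 | 1/5 | 0.067 |
| Four laser losses, no control losses | 12/19 | 1/5 | 0.112 |
| Four losses per arm, all non-response | 12/19 | 1/9 | 0.013 |
| Four losses per arm, lost controls as responders | 12/19 | 5/9 | 0.51 |

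In the fifth row the rate difference falls from 80 − 20 = 60 points to 63 − 11 = 52 points, yet p also falls, because 44% of controls but only 21% of laser subjects are set to failure. For 9 v 0 it takes three laser-only losses to pass 0.05 (9/17, p = 0.049; 9/18, p = 0.060).

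**False-positive rate in an adverse case.** Suppose both arms have a true 50% response rate, 19 laser subjects and 5 controls are randomized, four laser non-responders are dropped and no controls are lost. Exact enumeration gives a one-sided type I error of 0.060, against 0.021 with all 24 analysed. The apparent laser rate becomes 63%.

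**Section 3.3.2.1 against the rest.** It excludes subjects who are enrolled but not treated. Section 4.1 gives controls no treatment. Section 13.2 plans five evaluable controls, qualified by study visits rather than treatment, and 13.3.2 estimates and compares both arms. Read literally, 3.3.2.1 leaves a control n of 0 and no comparison.

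**The case against.** The strongest reply concerns direction. A reader might infer that the rule biases the test toward the laser. The documents do not support that as a certainty. The rule applies to both arms in the same words, and 13.2 expects equal numbers lost, hence a larger share of controls. Counting all eight losses as non-responders makes the laser result stronger: 12 v 1 moves from 0.031 to 0.013, and 11 v 1 from 0.058 to 0.024 (11/19 v 1/9). The 0.112 adds back laser losses only; with just two control losses also counted as non-response it is 0.037 (12/19 v 1/7). This objection stands. It limits the claim to a possible bias of unsettled direction, and it shows that imputing every loss as failure cannot be the only all-randomized analysis.

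Progression, the one withdrawal that directly shows lack of efficacy, is kept as non-response in both arms (4.0 and 13.2). A subject who stops for toxicity has an unknown response, so calling it failure is a choice of estimand. That is fair, but the plan makes the opposite choice by exclusion and shows no alternative.

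A reader might also infer that 3.3.2.1 is meant to discard the control arm. Sections 13.2 and 13.3.2 make the contrary intent plain; it is a drafting contradiction, and its literal effect would be no comparison rather than a biased one.

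Nor do the documents show that ineligibility will be used selectively after randomization. Section 12.0 does say "Subjects for whom documentation is inadequate to determine eligibility will generally be deemed ineligible", but 3.3.2 and 3.3.3 require eligibility to be signed off and confirmed before registration and randomization.

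Finally, this is a pilot, and over-enrolment to reach an evaluable number is stated openly. That lowers the severity. It does not remove the problem, because the plan still specifies a randomized test.

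**Conclusion.** The concern holds as a risk. The only planned analysis set removes laser subjects who stop for toxicity or intolerance, through a route that controls do not have. It can overstate the laser response rate: 80% against 63% with 12 responders and four losses as non-response. It can also bias the comparison in either direction. For 12 v 1 observed responders and four losses per arm, p runs from 0.013 to 0.51 according to how lost controls are counted; the plan would report only 0.031.

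These figures assume one BCC per subject, four losses per arm as implied by the maximum of 28, and lost laser subjects as non-responders. The documents give no split of losses by reason, so the range is the result, not any single row. The contradiction between 3.3.2.1 and sections 4.1, 13.2 and 13.3.2 is definite and needs correcting in its own right. Severity: should-fix for a pilot.

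**What to change.** 1. In 13.2 and 13.3.2, analyse all randomized subjects in their assigned arm. Count laser subjects without a Day 84 classification as non-responders, and show lost controls both as non-responders and as responders.
2. If the per-lesion analysis in 13.3.2 applies, handle all qualifying BCCs of a lost subject in the same way.
3. Keep the evaluable set as a further analysis, and report losses by arm and reason.
4. Delete the sentence in 3.3.2.1 on enrolled but untreated subjects, or limit it so that it does not reach controls. If a limited version is kept, it should not override item 1 for subjects randomized to the laser who leave before the first session.
5. Reconcile 5.4, under which related toxicity of grade III or higher leads to consideration of removal, with 11.2, under which related grade III toxicity leads to withdrawal. The two passages decide who becomes non-evaluable.

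The cost is wording and a few tables, with no new subjects, visits or data. The reported laser response rate will be less favourable if laser subjects are lost.

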## 4.0 TREATMENT PLAN

Subjects in the treatment arm will receive 3 treatments using the 595/1064 multiplex laser spaced by a four week interval (+/- 7 days), administered in an outpatient clinic setting. If a subject in the treatment arm has multiple BCCs satisfying inclusion criteria, all BCCs will be treated. The treatment settings for this laser will be as follows:

595 nm PDL at a fluence of 10 J/cm^2, a 10 ms pulse duration, and a 10 mm spot size, followed by 500 ms multiplex interpulse delay, followed by 1064 nm laser at a fluence of 40 J/cm^2, 10 ms pulse duration, and 10 mm spot size; the BCC lesion will be treated using 10% overlap with a single pass, along with 4 mm of normal skin. Dynamic cooling feature (cool air being blown onto treatment area) will be provided.

Subjects in the control arm will receive 3 regular study visits spaced 4 weeks (+/- 7 days) apart. If a subject in the control arm has multiple BCCs satisfying inclusion criteria, all BCCs will not be treated.

Four weeks (+/- 7 days) after the last (Day 84) both treatment and control patients will be assessed for final clinical appearance, measurement, and evaluation of the lesion by a dermatologist. Perpendicular diameters of the lesion will be measured with a ruler, as on initial evaluation, and surface area will be calculated. Residual tumor burden will be calculated based on change in surface area of the lesion.

Subjects will also undergo deep excisional biopsy encompassing the entire lesion to determine residual tumor cell presence. If histologic examination of the tissue reveals residual BCC, then the subject will receive standard of treatment.

A digital camera will be used to photograph the BCC immediately before, during and after treatment.

**Note:** If any clinical signs of progression are visible during this period (what we will consider greater than 10% growth), the subject in either treatment arm or control arm will be withdrawn from the study and undergo standard of care. Such a subject will be considered non-responder for the efficacy analysis.

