## 5.2 Evaluations during treatment

After enrollment (day 0), subjects in both control and treatment arms will receive standard baseline photographs of their lesion. Subjects in the treatment arm will receive their first laser treatment. Lesions will be assessed by [name] and documented, as well as monitoring for adverse effects and reviewing "prohibited" medications.

Days 28 and 56 (+/- 7 days) correspond to treatment sessions #2 and #3 for the treatment arm, and study visits #2 and #3 for the control arm. At these visits, patients will be asked of any side effects, reactions, or adverse events that occurred since the last visit as well as any other concerns. These will all be documented. If any serious adverse events have occurred, they will be reported to the IRB as per University of Miami policy.

Photographs and measurements of the lesion will be taken at each study visit. Subjects in the treatment arm will then receive laser treatment and patients in the control arm will receive a standard study visit.

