### 9.5 Response Review

Final response review will be conducted four weeks after the last of 3 treatment sessions for the treatment arm or the last of 3 study visits for controls.

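### Section 13.2 drops subjects who miss a Day 28 or Day 56 visit or session even when their Day 84 primary outcome was observed

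*Combined protocol and SAP*

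**What the plan says.** Section 13.2 defines the analysis set. Apart from subjects withdrawn for PD, who count as non-responders, a subject must "complete three treatments/three study visits and the biopsy" visit. The same section then lists the grounds for non-evaluability, ending with "or they cannot complete treatments or study visits for any reason other than PD". The targets of 15 laser and 5 control subjects are counts after these exclusions, and enrolment may go up to 28 to reach them.

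The interim visits are part of the required three. Section 5.2 says Days 28 and 56 "correspond to treatment sessions #2 and #3 for the treatment arm, and study visits #2 and #3 for the control arm". For controls they carry no intervention: Section 4.1 says these subjects "will not receive any treatment; however they will receive 3 regular study visits spaced 4 weeks" apart.

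The outcome is scored once. Section 9.5 states: "Final response review will be conducted four weeks after the last of 3 treatment sessions for the treatment arm", with the matching time point for controls. Section 4.0 places this at Day 84, when "both treatment and control patients will be assessed for final clinical appearance, measurement, and evaluation of the lesion by a dermatologist", followed by excision of the whole lesion. Sections 9.1 and 9.2 classify response from lesion size relative to baseline and from histology.

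**The concern.** Being analysed depends on something the endpoint does not use. A control who skips Day 28 but attends Day 84 has a baseline size, a final size and a histology result, and can be placed in the Section 9.2 table. Section 13.2 still removes that subject. A laser subject who misses one session and attends Day 84 is removed in the same way. Neither has a missing outcome.

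The exclusion is decided after randomization, by behaviour that may differ between arms, with everyone aware of the assignment. In the laser arm, a subject who misses a session and does not respond leaves the denominator, which can raise the reported response rate. In the control arm each subject is one of a planned five, so a discarded outcome can matter to the test.

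**Working it through.** **1. Is the outcome scorable without the interim visits?**

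- The Section 9.2 table has two inputs: size category relative to baseline, and histology. Both are available from Day 0 and Day 84.
- Interim measurements enter the endpoint only if they show PD (Sections 4.0 and 11.1). Otherwise they feed the descriptive plots in Section 13.3.1.
- A missed visit is not a listed withdrawal reason in Sections 11.1 to 11.4. Section 3.3.2.1 says a subject who does not complete therapy may withdraw; it does not require it. Such a subject can therefore reach Day 84.
- Section 13.3 contains no all-randomized analysis and no sensitivity analysis.

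**2. The plan's own p-values.** With N subjects in total, R responders in total, m controls and b control responders, the one-sided Fisher value is

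p = Σ(x=0..b) C(R,x)·C(N−R, m−x) / C(N,m).

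- 11/15 v 1/5: (56 + 12×70)/15504 = 896/15504 = 0.058
- 12/15 v 1/5: (21 + 13×35)/15504 = 476/15504 = 0.031
- 9/15 v 0/5: 462/15504 = 0.030

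All three agree with the table in Section 13.2. Like that table, everything below assumes one BCC per subject.

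**3. One control lost and not replaced, laser arm held at 15.** The denominator is C(19,4) = 3876.

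| Laser v control | Calculation | p |
|---|---|---|
| 12/15 v 1/4 (non-responder lost) | (15 + 13×20)/3876 | 0.071 |
| 9/15 v 0/4 (non-responder lost) | 126×(210/126)/3876 = 210/3876 | 0.054 |
| 12/15 v 0/4 (responder lost) | 35/3876 | 0.009 |
| 13/15 v 1/4 (one more laser responder) | (5 + 14×10)/3876 | 0.037 |
| 10/15 v 0/4 (one more laser responder) | 126/3876 | 0.033 |

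**4. The laser side.** Suppose one further laser subject missed a session, was assessed on Day 84 and did not respond. Dropped, the rates stay at 12/15 = 80% and 9/15 = 60%. Kept, they are 12/16 = 75% and 9/16 = 56%, with p = 966/20349 = 0.047 against 1/5 and p = 792/20349 = 0.039 against 0/5. The rule can therefore move the result in either direction.

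**5. Can over-enrolment absorb the losses?** The maximum of 28 equals 15+4+5+4, which implies 9 controls. Section 3.3.3 randomizes 3:1, which gives 28×1/4 = 7. Section 13.2 expects three to four non-evaluable subjects in each arm, for all reasons. That leaves 7−3 = 4 or 7−4 = 3 controls. With three controls (denominator C(18,3) = 816), 12/15 v 1/3 gives 140/816 = 0.172 and 9/15 v 0/3 gives 84/816 = 0.103.

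**The case against.** **Replacement.** Five is an evaluable count and the plan over-enrols, so one exclusion does not automatically turn 15 v 5 into 15 v 4. This stands, and the illustrative p-values are conditional on no replacement. It is not a full answer: 3:1 allocation of 28 yields about 7 controls, and replacement restores the count without restoring the discarded outcomes.

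**The reversal.** A reader might infer that losing any one control overturns both results the plan calls significant. The figures do not support that. The lost control must be a non-responder, must not be replaced, and the laser count must sit exactly at the plan's threshold. Section 13.2 itself speaks of twelve or more and nine or more responders.

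**Imbalance.** A reader might also infer that missed visits will fall mainly on controls, since the same expected three to four non-evaluable subjects are a larger share of a smaller arm. That allowance covers every reason for non-evaluability and says nothing about subjects who miss an interim visit yet attend Day 84. That subgroup could be empty.

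**Incomplete PD checks.** Interim visits are where growth before Day 84 is seen, so a subject who skips one has had one fewer check. This is true. But a lesion at 110% of baseline or more on Day 84 is still scored PD, so the endpoint remains scorable.

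**Timing.** Section 9.5 counts from the last of three sessions, which could leave the assessment time unclear after a skipped session. Section 5.3 and Appendix I fix it at Day 84 with a 7-day window.

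**A deliberate completer set.** A pilot may reasonably ask what a full three-session course achieves. That supports reporting the completer rate. It does not justify making it the only analysis of a randomized comparison, and it gives no reason to drop controls for missing visits at which nothing is given.

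**Conclusion.** The point holds as a defect in the analysis-set definition. Read literally, Section 13.2 discards observed primary outcomes after randomization, and no other planned analysis brings them back. This rests on the text alone.

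Its numerical effect cannot be estimated, because the documents give no rate for missed interim visits among subjects who reach Day 84. The shifts from 0.031 to 0.071 and from 0.030 to 0.054 show how sensitive the test is to one non-responding control lost without replacement at the threshold counts. They are not a forecast. Other cases leave the result significant (0.037 and 0.033) or strengthen it (0.009). For a pilot this is a worthwhile correction and does not undermine the design.

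**What to change.** In Section 13.2, define the primary analysis set as eligible randomized subjects, in their assigned arm, who have baseline and Day 84 lesion assessments and Day 84 histology, or PD before Day 84, regardless of missed interim visits or sessions. Remove incomplete treatments or visits as a ground for non-evaluability when Day 84 was attended. Keep the set that completed all three as a sensitivity analysis, and report missed visits and sessions by arm.

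Two other passages must be reconciled with this wording. Section 3.3.2.1 excludes enrolled but untreated subjects from all analyses; taken literally this would also catch the control arm, which is untreated by design. Section 4.2.1 says subjects who start a prohibited medication are either removed or counted as inevaluable for response, without saying how the choice is made for the analysis.

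The cost is wording only: no change to treatment, visits or sample size. The laser response rate may be slightly less favourable because it will include any under-treated subjects, and a subject with a missed visit will have had one fewer interim check for PD.

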#### **13.3.2 Efficacy**

Each BCC will be assessed for response as specified in Section 9.0.

If all subjects have one BCC, the overall response rates (CR or PR) for treatment and control arms will be estimated by the percentage of subjects achieving these criteria and compared using one-sided Fisher's exact test. The corresponding two-sided 95% confidence intervals will be estimated by the exact binomial method.

If some study subjects have more than one BCC, response rate will be defined as the number of BCCs achieving CR or PR divided by total number of BCCs for all subjects in each arm. We will use Donner's adjusted  $\chi^2$  test with one degree of freedom to compare response rates between the treatment and control arms. The corresponding two-sided 95% confidence intervals will be estimated using Jung and Ahn's method. We also report percentage change in lesion size for both treatment and control arms.

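### The primary response rate covers only completers and progressions (13.2), and 13.3.2 plans no sensitivity analysis for the other early leavers, so the laser rate is likely too high if leavers do worse

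*Combined protocol and SAP*

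**What the plan says.** Section 13.2 defines evaluable subjects as those who are eligible and either complete the three treatments or visits and the biopsy visit, or are withdrawn for progressive disease (PD). Everyone else is left out: "Subjects will be non-evaluable when they do not wish to continue in the study", when they are unable to continue, or when "they cannot complete treatments or study visits for any reason other than PD". The reason for leaving plays no part.

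The section fixes 15 evaluable laser and 5 evaluable control subjects, allows for losses ("We expect that three to four subjects in both treatment arm and control arm will be non-evaluable"), and sets maximum enrolment at 28. The protocol does not speak of replacing subjects, but a fixed evaluable number with over-enrolment has that effect.

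Progression is the one early exit counted as failure. Section 4.0 says of a subject withdrawn for growth: "Such a subject will be considered non-responder for the efficacy analysis".

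Response is judged at Day 84 (9.5: "Final response review will be conducted four weeks after the last of 3 treatment sessions"). Section 13.3.2 then states that "the overall response rates (CR or PR) for treatment and control arms will be estimated by the percentage of subjects achieving these criteria", with a one-sided Fisher's exact test and exact intervals, or Donner's test with Jung and Ahn intervals if some subjects have several BCCs. It plans no sensitivity analysis.

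**The concern.** Under 9.2, stable disease is not a response, so a laser subject whose lesion is unchanged at Day 84 counts as a failure. If the same subject gives up at Day 56, 13.2 takes that subject out of the denominator.

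Such an exit is possible. The trial is unblinded (3.3.3), and lesions are followed openly (5.2: "Photographs and measurements of the lesion will be taken at each study visit"). Subjects may leave at any time (11.3), and the investigator may withdraw a subject if treatment is judged inappropriate (11.4). Section 6.1 adds, with no time point: "Should our treatment prove ineffective, all patients will receive standard treatment of care immediately". Two other routes also lead to non-evaluable status: withdrawal for related grade III toxicity (11.2) and removal for starting a prohibited medication (4.2.1).

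The response rate is the primary endpoint and is meant to inform whether the laser merits further study (13.1). Its exact interval is computed on the same selected set. The plan expects three to four exclusions per arm against 15 and 5 evaluable subjects, so how they are handled can matter.

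**Working it through.** **Inputs (13.2, 13.3.2).** 15 laser and 5 control evaluable subjects; three to four non-evaluable per arm; one-sided Fisher's exact test; two-sided 95% exact (Clopper-Pearson) intervals; one BCC per subject, as in the 13.2 table.

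**Reproducing the plan.** Enrolment: 15 + 5 + 4 + 4 = 28, as stated. One-sided Fisher p-values: 11/15 v 1/5, 0.0578; 12/15 v 1/5, 0.0307; 9/15 v 0/5, 0.0298. These match the printed 0.058, 0.031 and 0.030.

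**Laser rate.** With r responders among the 15 evaluable subjects and k early leavers counted as failures, the rate is r/(15 + k). The documents do not give k. The range 0 to 4 is assumed, with 4 being the plan's allowance for all causes, so it is a ceiling and not an estimate.

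| k | 12 responders (exact 95% CI) | 11 responders |
|---|---|---|
| 0 | 12/15 = 80.0% (51.9 to 95.7) | 11/15 = 73.3% |
| 1 | 12/16 = 75.0% (47.6 to 92.7) | 11/16 = 68.8% |
| 2 | 12/17 = 70.6% (44.0 to 89.7) | 11/17 = 64.7% |
| 3 | 12/18 = 66.7% (41.0 to 86.7) | 11/18 = 61.1% |
| 4 | 12/19 = 63.2% (38.4 to 83.7) | 11/19 = 57.9% |

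**Direction.** If j of the k leavers would have responded by Day 84, the full rate is (r + j)/(15 + k). The evaluable rate r/15 is too high exactly when j/k is below r/15, that is, when leavers do worse than those who stay. With r = 12 and one leaver who would have responded, the full rate is 13/16 = 81.3%, and dropping that subject lowers it to 80.0%.

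**Between-arm p-value.** Starting from 12/15 v 1/5 (p = 0.031), with exits counted as failures:
- one laser exit only: 12/16 v 1/5, p = 0.048
- two laser exits only: 12/17 v 1/5, p = 0.067
- one exit in each arm: 12/16 v 1/6, p = 0.023
- one control exit only: 12/15 v 1/6, p = 0.014
- four exits in each arm: 12/19 v 1/9, p = 0.013

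Starting from 11/15 v 1/5 (p = 0.058), one exit in each arm gives 11/16 v 1/6, p = 0.043.

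**Whether other sections repair this.** Section 13.3.1 plans lesion size by visit and a spider plot, but does not re-estimate response. Section 13.5 says excluded data will be reported, and 14.4 asks for source notes on response at early termination. None requires exits by arm and reason, and none returns these subjects to a denominator.

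**The case against.** The exit in question is hypothetical. No section directs withdrawal for lack of response. Sections 4.0, 5.3 and 9.5 place response review at Day 84 and standard care after it, and the sentence in 6.1 can be read in that light. Involvement lasts about 13 weeks and every lesion is to be biopsied at Day 84, so a subject gains little by leaving early. Growth of 10%, the objective failure, is already counted. This stands: the number of such exits may be zero.

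At Day 28 a subject has had one of three sessions and at Day 56 two, and partial response needs only a 10% reduction. A lesion that looks unchanged then is not an observed Day 84 failure. This also stands: counting it as one is imputation.

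A reader might infer that dropping these subjects can only raise the laser rate. The 13/16 example shows otherwise. A reader might also infer that the rule produces a false-positive comparison. The documents do not support that, because control exits are dropped as well and, with equal exits, the current rule is conservative for the test.

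A reader might want to rewrite the primary rule so that leaving for non-response counts as failure. That reason would be assigned unblinded, and untreated control lesions are unlikely to regress, so the change could favour the laser in the comparison (0.058 to 0.043 above). The present rule rests on a measured criterion, and that is a fair reason to keep it for the primary analysis.

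Finally, this is a pilot with a disclosed evaluable set and no response-rate threshold for going further. That limits the weight of the point, but not the value of showing how far the rate depends on the exclusions.

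**Conclusion.** The point holds as a gap in the analysis plan. The primary response rate describes completers and progressions only, and nothing planned shows how it would look with the other early leavers included. If leavers do worse than those who stay, the laser rate is likely overstated. With 12 responders, the overstatement is 5.0 percentage points for one exit counted as a failure (80.0% to 75.0%) and 16.8 points at the ceiling of four (80.0% to 63.2%). These figures assume one BCC per subject and that the leavers counted are failures. The documents establish neither the number of leavers nor their outcomes. No direction is claimed for the between-arm p-value. This is an inexpensive improvement and not a fault that invalidates the design.

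**What to change.** Keep the 13.2 evaluable set as the primary analysis. Then:

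1. Add to 13.3.2 a prespecified sensitivity analysis of all eligible randomised subjects in either arm who attended the Day 0 visit. Count those with no Day 84 assessment, for any reason, as non-responders, with all their BCCs if they have several.
2. State that this includes related grade III toxicity withdrawals (11.2) and prohibited-medication removals (4.2.1), and that the exclusion of untreated subjects in 3.3.2.1 does not remove controls.
3. Show the response rate and exact interval by arm beside the primary result, or the Jung and Ahn interval if some subjects have several BCCs. Because imputing failure in both arms can lower the p-value, do not use this analysis to claim significance.
4. Report early exits by arm and reason.

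The cost is a few sentences in 13.3.2 and a line in the disposition table, with no extra visits or subjects and no change to when a subject may leave. The downside is that some leavers with an unknown Day 84 outcome are imputed as failures, and the reported laser rate may look less favourable.
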